**Part A: Dose Escalation**

	Period 1		Period 2		Period 3	
Cohort 1 (n=9) (LY=6; PL=3)	Dose 1, 0.3 mg LY or PL	≥14 d washout	Dose 3, 3 mg LY or PL	≥14 d washout	Dose 5, 30 mg LY or PL	≥14 d washout
Cohort 2 (n=9) (LY=6; PL=3)		Dose 2, 1 mg LY or PL	≥14 d washout	Dose 4, 10 mg LY or PL	≥14 d washout	Dose 6, 100 mg LY or PL

Part A: Safety review to be completed after each dose level, prior to escalation. From **Dose 4 onwards**, PK data review to be completed prior to dose escalation.

**Part B: Serial CSF Sampling**

	Period 1
Cohort 3 (n=7) (LY=5; PL=2)	Dose B1 or Placebo
Cohort 4 (n=7) (LY=5; PL=2)	Dose B2 or Placebo
Cohort 5 (n=7) (LY=5; PL=2)	Dose B3 or Placebo

Dose B1 will be determined by PK/PD data through Part A Dose 2, and safety data through Part A Dose 4.

Dose B2 will be determined by:

- PK/PD data from Dose B1
- PK/PD data from Part A Dose 4
- Safety Data through Part A Dose 5.

Dose B3 will be determined by:

- Maximum tolerated dose from Part A.
- PK data from Part A.
- PK/PD data from Doses B1 and B2.

**Part C: Itraconazole Interaction**

	Period 1		Period 2		
Cohort 6 (n=8) (LY=8, Itra = 8)	LY	≥7 d washout	Itra (7 doses)	LY + Itra	Itra (5+ doses)

Abbreviations: CSF = cerebrospinal fluid; d = day; Itra = itraconazole; LY = LY3323795; PD = pharmacodynamics; PK = pharmacokinetics; PL = placebo; TBD = to be determined.

**Figure SCAA.1. Illustration of study design for Protocol I9F-MC-SCAA.**

### **5.1.1. Part A: Dose-Escalation Study**

Part A is a dose-escalation study that will be conducted in 2 alternating cohorts (Cohorts 1 and 2), each consisting of approximately 9 subjects (6:3 subjects, LY3323795:placebo at each dose level) who will participate in 3 study periods (total of 6 dose levels in the 2 cohorts). The number of subjects intended to be enrolled is detailed in Section 5.2. The first 4 dose levels of LY3323795 are anticipated to be 0.3 mg, 1 mg, 3 mg, and 10 mg. Doses 5 and 6 are anticipated to be 30 and 100 mg, but will be confirmed following PK data reviews. See Section 5.1.1.1 for details of dose-escalation decisions.

Sentinel dosing will be used in this study. For all dose levels, LY3323795 and placebo will be administered first to a sentinel group of 2 subjects (1:1, LY3323795:placebo). These subjects will be followed for 24 hours postdose; if the dose is well tolerated, dosing of the remaining 7 subjects in the cohort may begin.

The proposed dose levels may be adjusted based on emerging safety and PK data (see Section 7.4.1).

Subjects will be admitted to the CRU on Day -1 (see Part A Schedule of Activities, Section 2) and will remain as inpatients for at least 48 hours after dosing on Day 1, after which they may be discharged at the discretion of the investigator. Subjects will then return for outpatient visits for up to 144 hours postdose (Day 7). The washout time between doses for a given subject will be at least 14 days.

PK and PD (plasma A $\beta$ ) data, as well as safety assessments, including clinical laboratory tests, ECGs, AEs, vital signs, ophthalmic examinations, and neurological surveys, will be collected at various time points pre- and postdosing with LY3323795/placebo, as described in Part A Schedule of Activities (Section 2). However, exact time points for PK/PD and safety assessments may be modified based on interim PK/PD results (see Section 5.1.1.1).

#### **5.1.1.1. Dose Escalation and Interim Access to Data in Part A**

The decision to dose escalate will be based on safety reviews conducted after each dose (and PK reviews from Dose 4 [planned to be 10 mg] onwards). Dose escalation will not occur until after a review of at least 3 days' safety data from the preceding dose level has been carried out, and the dose shown to be safe. Accordingly, safety data, including AEs, vital signs, neurological surveys, ophthalmic tests, ECGs, and clinical laboratory tests, will be assessed by both the investigator and the sponsor prior to each dose escalation. Any available PK data may be reviewed but PK data are not required for the initial dose-escalation decisions. However, from Dose 4 onwards, LY3323795 PK data will be reviewed before escalation to the next subsequent dose level to verify that the projected median exposure does not exceed one tenth the NOAEL exposure established in rats (i.e. median area under the concentration-versus-time curve (AUC) will not exceed 3,450 ng $\cdot$ hour/mL and median Cmax will not exceed 214 ng/mL) (see Section 7.4.1). PK samples up to 96 hours postdose will be required to conduct the PK data reviews. The 96-hour PK sampling period may be adjusted based on emerging PK data. Plasma A $\beta$  data may also be reviewed to assess the PD profile. Time points for PK and PD sampling and required safety assessments may be modified based on emerging PK and safety results.

In addition to the reviews of PK data required after Dose 4 for the purposes of dose escalation, interim access to PK and PD (including plasma A $\beta$ ) data will occur after the anticipated 1-mg dose (Dose 2) and 10-mg dose (Dose 4) of Part A. Data from this interim access to data (IAD) reviews, as well as results of the PK IADs following Doses 4, 5, and 6, will be used at different points to select doses in Part B (see [Figure SCAA.1](#)).

### **5.1.2. Part B: CSF Sampling Study**

Part B is a single-dose, 3-cohort (5:2 subjects, LY3323795:placebo per cohort), single-period, lumbar catheter study to evaluate central PK/PD of LY3323795. See Section 5.2 for planned enrollment numbers. Part B may be conducted in parallel to Part A of the study, as long as the conditions have been met for each dose decision in Part B (see Section 5.1.2.1).

Subjects will be admitted to the CRU on Day -1 and will remain as inpatients until at least 24 hours after the CSF catheter is removed, after which they may be discharged at the discretion of the investigator. CSF will be collected from an indwelling catheter using a closed system. The catheter will be inserted approximately 4 hours prior to study drug administration. CSF samples will be taken during this “stabilization” period approximately every 2 hours, as feasible. If some samples during the stabilization period are not collected for any reason, this will not be considered a protocol violation.

CSF PK and PD data will be collected by frequent sampling for 4 hours predose and up to 36 hours postdose (as described in the Part B Schedule of Activities, Section 2). The minus 4-hour CSF sample will be collected for safety (red blood cell count, glucose, and protein, to be tested at the local laboratory) and PD biomarkers (which will be tested centrally). The minus 2-hour sample will be collected for PD biomarkers only; the 0-hour and subsequent postdose samples will be collected for LY3323795 concentration and PD biomarkers. An additional safety CSF sample will be collected at the removal of the catheter. CSF PD samples will be split and stored

CCI

Plasma PK and PD (plasma A $\beta$ ) data will be collected up to 144 hours postdose (as described in the Part B Schedule of Activities, Section 2).

Safety assessments including clinical laboratory tests, ECGs, AEs, vital signs, ophthalmic examinations, and neurological surveys will be collected (as described in the Part B Schedule of Activities, Section 2).

Two IAD reviews are planned in Part B: the first after the completion of dosing for Cohort 3 and the second after dosing for Cohort 4. All CSF PK/PD data will be included in these reviews, as well as plasma PK data through Day 4. See Section 5.1.2.1 for details.

#### **5.1.2.1. Dose Selection and Pharmacokinetic Analysis in Part B**

Any dose selected for administration in Part B will be less than or equal to doses previously administered and found to be well tolerated in Part A. Emerging PK data (and PD data, as available) from the first 2 doses in Part A, and safety data through Dose 4 of Part A, will determine Dose B1 for Cohort 3.

### Cohort 3

Cohort 3 is intended to gauge the degree to which LY3323795 crosses the blood-brain barrier. A 3-mg dose is intended to be administered in Cohort 3, if supported by Part A data. Modeling of nonclinical data suggests that this dose would result in CSF LY3323795 concentrations exceeding the lower limit of quantification (approximately 0.1 ng/mL) for at least 12 hours. This dose may be modified if Part A data suggest that the plasma exposure of LY3323795 is meaningfully different from the nonclinical predictions.

### Cohorts 4 and 5

The dose for Cohort 4 will be selected based on data from Cohort 3, specifically the plasma and CSF PK/PD data, alongside data from Part A. The dose for Cohort 5 will also depend on these data from Cohort 3 and Part A, in addition to data from Cohort 4 (see [Figure SCAA.1](#)). Doses estimated to produce substantial reductions in CSF A $\beta$  concentrations will be selected, with the goal that at least 1 of these doses will produce reductions in CSF A $\beta$  of >50% (relative to baseline) for at least 4 hours. In no case will the doses selected exceed the maximum tolerated dose (MTD) found in Part A.

### **5.1.3. Part C: Itraconazole Interaction Study**

Part C is an open-label, fixed-sequence, single-cohort study in 8 healthy subjects to evaluate potential CYP3A4 interaction when LY3323795 is coadministered with itraconazole. Part C is divided into 2 periods.

In Period 1, subjects will be administered a dose of LY3323795 (intended to be 3 mg); the dose will be at or below a level previously administered safely in Part A. There will be a washout period of at least 7 days following this dose, with PK assessed up to 144 hours postdose.

In Period 2, subjects will be dosed with itraconazole for 6 consecutive days prior to coadministration with LY3323795. On Day 10, subjects will receive itraconazole 200 mg twice, approximately 12 hours apart. On Day 11, subjects will receive a morning dose of itraconazole 200 mg prior to discharge. On Days 12 to 14, subjects will attend the CRU on an outpatient basis and will receive doses of itraconazole 200 mg once daily in the morning. On Day 15, subjects will be re-admitted to the CRU and will receive a single dose of itraconazole 200 mg. On Day 16, subjects will be administered 200-mg itraconazole 1 hour prior to receiving LY3323795 (using the same LY3323795 dose administered in Period 1). The timing may be adjusted based on available PK results from Part A. All subjects in the cohort will receive LY3323795; there will be no placebo. From Day 17 onwards, it is intended that subjects will receive daily doses of 200-mg itraconazole alone for 5 days; based on emerging PK data, this period of daily itraconazole dosing may be extended to ensure that CYP3A inhibition is maintained throughout the elimination of LY3323795. Based on the projected half-life of LY3323795 (23 hours), 168 hours of sampling allows more than 3 half-lives of coverage in the event that clearance doubles; this would be sufficient to characterize a doubling in clearance.

Samples will be collected to assess itraconazole PK on the day of dosing with LY3323795 (see Part C Schedule of Activities [Section 2]). Exact time points for PK/PD and safety assessments may be modified based on emerging PK/PD results.

## 5.2. Number of Participants

For Cohorts 1 and 2 in Part A, up to approximately 24 subjects may be enrolled so that approximately 18 subjects (9 subjects per cohort [6:3, LY3323795:placebo per dose level]) complete the study.

For Cohorts 3 to 5 in Part B, up to approximately 30 subjects may be enrolled so that approximately 21 subjects (7 subjects per cohort [5:2, LY3323795:placebo]) complete the study.

For Cohort 6 in Part C, up to 12 subjects may be enrolled so that approximately 8 subjects complete the study.

Subjects in 1 part of the study will not be allowed to participate in any other part of the study.

Subjects will be replaced as needed, rather than over-enrolled. See Section 10 for details on the replacement of subjects.

## 5.3. End of Study Definition

The end of the study is the date of the last visit or last scheduled procedure for the last subject, as shown in the Schedule of Activities (Section 2).

## 5.4. Scientific Rationale for Study Design

This study will be conducted to determine the safety and tolerability of LY3323795 in healthy subjects.

The crossover design in Part A of this study will allow each subject to act as their own control and allow for an assessment of within- and between-subject variability in evaluating tolerability and PK of different doses of LY3323795. The placebo-controlled, dose-escalation strategy allows safety and PK/PD data to be obtained with a large degree of within-subject control data.

The collection times for PK samples and washout period between doses are based on the predicted PK and PD of LY3323795 from nonclinical studies. Based on the estimated half-life of approximately 23 hours, sample collection for up to 144 hours should be sufficient to fully assess the concentration-time profile, and a washout period of at least 14 days should be sufficient to ensure that there is no carryover between periods. Either or both may be revised based on reviews of preliminary PK data generated during the study.

It is intended that a range of 3 doses of LY3323795 be administered in Part B of the study based on the LY3323795 exposures and plasma PD response observed in Part A. The aim is to determine a dose level that produces a substantial reduction in CSF A $\beta$ . The exact doses of LY3323795 administered in Part B will be determined after reviewing the emerging data from Part A, as well as available data from any previous doses carried out in Part B. However, doses in Part B will not exceed a dose that has been assessed in Part A as being safe and well tolerated.

To minimize confounding effects of the catheterization on A $\beta$  concentrations, the indwelling catheter for CSF collection will be inserted approximately 4 hours prior to study drug administration to allow A $\beta$  CSF measurements to stabilize. Previous CSF catheter studies have shown large variability in CSF A $\beta$  in the first few hours of collection after catheterization (Ereshefsky et al. 2007).

In healthy subjects, CSF indwelling catheter studies conducted by Lilly have shown increases in CSF A $\beta$  concentration over 24 to 40 hours of sampling (Lucey et al. 2015). In these CSF catheter studies, the initial 4-hour sampling interval following the catheter placement showed a 10% to 15% increase in A $\beta$  concentration. Subjects receiving placebo following the catheter placement showed additional increases of 20% to 30% over a 36-hour CSF sampling period. Similar findings were shown by Bateman (2008). Therefore, placebo will also be included in Part B of this study. Previous studies have also shown that CSF A $\beta$  concentrations slowly return to baseline following a treatment that disrupts A $\beta$  synthesis; however, due to the large variability in CSF A $\beta$  concentrations both within and between individuals, a long duration of sampling is required to fully characterize the PD time course.

An assessment of LY3323795 PK with concomitant itraconazole administration is planned in Part C. In vitro recombinant CYP isoform phenotyping studies indicate CYP3A4 is the only tested CYP isoform that metabolizes LY3323795. In vitro metabolism studies with human hepatocytes suggest that CYP-mediated metabolism accounts for approximately 70% of the overall metabolism in hepatocytes. Taken together, these data result in a predicted LY3323795 AUC increase of approximately 4-fold when LY3323795 is coadministered with the strong CYP3A inhibitor itraconazole. Accordingly, coadministration with itraconazole will help determine the clinical relevance of CYP3A inhibition on LY3323795 clearance. The dosing regimen for itraconazole was optimized using a physiologically based PK model with the goal of reaching steady-state concentrations as rapidly as possible (Ke et al. 2014). The use of the oral solution formulation of itraconazole is specified as it has higher bioavailability and less variability in absorption than solid dosage formulations.

## 5.5. Justification for Dose

This study will evaluate plasma and CSF PK/PD of LY3323795 in an attempt to define a pharmaceutically relevant dose range for future studies. The initial proposed dose is 0.3 mg, which is anticipated to provide a maximum drug concentration ( $C_{max}$ ) of 0.625 ng/mL (90% confidence interval [CI]: 0.36, 1.11), and an area under the curve from time 0 extrapolated to infinity ( $AUC_{[0-\infty]}$ ) of 24.5 ng·hour/mL (90% CI: 9.09, 65.9). This dose (by body surface area) is substantially lower than the dose levels identified as the NOAELs in 1-month GLP toxicology studies and is therefore appropriate for use (Table SCAA.2). The doses (based on body surface area) identified as the NOAELs in rats and dogs are 4,500- and 12,000-fold greater than the starting dose in humans. Margins calculated based on AUC exposure at the NOAELs relative to predicted human exposures at 0.3 mg are  $\geq 1,408$ -fold (due to a gender difference in exposure) in rats and 2,214-fold higher in dogs.

In a cardiovascular safety pharmacology study in dogs, no changes in QTc prolongation occurred at a dose of 0.5 mg/kg; this dose (based on body surface area) is 63-fold higher than the proposed starting dose in Study SCAA of 0.3 mg.

#### Part A

The doses studied in Part A will be selected to ensure that the exposures tested are anticipated to produce significant CSF A $\beta$  reductions at steady state. Based on nonclinical modeling, a plasma AUC of 1,800 ng•hour/mL (90% CI: 1240, 2600) is anticipated to produce a 90% time-averaged reduction in CSF A $\beta$  at steady state. Based on allometric scaling of clearance, it is anticipated that a dose of 22 mg (90% CI: 7.5, 63) will achieve this exposure. Accordingly, it is intended that doses of at least 100 mg will be explored to ensure that the full range of pharmacologically relevant exposures is tested in Study SCAA.

The upper dose in SCAA is projected to be 100 mg. However, assessments of PK at pre-specified times are planned during the dose escalation, and the anticipated doses may be modified to ensure that median exposures do not exceed one tenth of the rat NOAEL determined in toxicology studies (i.e. median AUC will not exceed 3,450 ng•hour/mL and median Cmax will not exceed 214 ng/mL).

#### Part B

Part B is an assessment of CSF PK/PD, with CSF collected over 36 hours following dose administration using a lumbar catheter. The initial dose in Part B is anticipated to be 3 mg, which is anticipated to produce measurable CSF LY3323795 concentrations. As described in Section 5.1.2.1, this dose may be increased if necessary, as long as the same dose level was well tolerated in Part A, to ensure that quantifiable LY3323795 concentrations are obtained. The maximum dose administered in Part B is intended to be the MTD in Part A, although a lower dose may be selected if indicated by emerging PK/PD data from either Part A or Part B.

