### 3.3. Benefit/Risk Assessment

Nonclinical safety information for LY3323795 adequately supports the transition from preclinical status to a clinical, single-dose study. On the basis of the nonclinical data, LY3323795 is not considered to be a high-risk compound. This protocol reflects the fact that LY3323795 has not been administered to humans previously, and to mitigate this risk, the study has been designed to be conducted in accordance with principles outlined in the Guideline on Strategies to Identify and Mitigate Risks for First-in-Human Clinical Trials with Investigational Medicinal Products (EMA 2007). Any identified risks are considered to be monitorable and

manageable at the anticipated dose range of 0.3 mg to 100 mg for LY3323795 in healthy subjects.

It is intended that sentinel dosing will be conducted at all dose levels in Part A to minimize risk to subjects (see Section 5.1.1 for details), in accordance with the clinical research unit's (CRU) procedures. Additionally, the PK of LY3323795 will be assessed at pre-specified time points during the study, to ensure that median exposures do not exceed the lowest NOAEL exposure in toxicology studies conducted under GLP (in male rats). In this study, there is no expected therapeutic benefit for the subjects.

The risks of CSF drainage via indwelling catheter are similar to those of lumbar puncture (LP) and are well known (Jhee and Zarotsky 2003). The most common side effect reported is headache. However, a vast majority of these headaches are mild to moderate in severity and respond to such first-line therapies as analgesia and hydration. Individuals with persistent headaches may respond to a single blood patch without sequelae. The rare persistence of headaches is thought to result from continued leakage of CSF from the area surrounding the needle insertion point. If a persistent severe headache occurs, a "blood patch" should be performed. This is done by injecting a small amount of the subject's blood into the region of the supposed leak to try to seal it. The blood patch procedure is effective in 95% of the cases for stopping the headache.

More information about the known and expected benefits, risks, serious adverse events (SAEs), and reasonably anticipated adverse events (AEs) of LY3323795 is to be found in the IB. Information on AEs expected to be related to the investigational product may be found in Section 7 (Development Core Safety Information) of the IB.

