## **7.4. Dose Modification**

### **7.4.1. Dose Decision/Escalation**

By nature of being a dose-escalation study, data will be evaluated on an ongoing basis until the MTD is determined or the highest planned dose (that is lower than the MTD) has been administered. The highest dose level that is tolerated will be designated as the MTD.

Safety data will be the primary criteria for the dose escalation. As described in Sections 5.1.1.1 and 5.1.2.1, certain dose-escalation decisions will also be based on PK ( $C_{max}$ , AUC, and clearance) data where available. No dose escalation can occur without prior discussion and agreement between the investigator and the Lilly clinical pharmacologist/CRP/study team.

Safety data, in particular AEs, SAEs, and adverse laboratory abnormalities, will be independently assessed by the investigator, and will be considered related to the investigational product unless there is clear evidence that the event is not related. See Section 10.3.1 for details.

After review of these data, an agreement on the appropriate dose escalation will be made by the investigator and sponsor for the next cohort. The magnitude of the dose escalation may be reduced following data review, but subsequent escalations cannot be increased by more than 3.3 times the original dose (a half-log increment).

If any of the following scenarios occur, dosing at the current level and further dose escalation will be discontinued:

- 1) a single subject experiences an SAE that is considered related to LY3323795 administration;
- 2)  $\geq 2$  subjects at the same dose level experience moderate or severe AEs that impair normal activities, and are considered related to LY3323795, but do not meet the CSE criteria;
- 3)  $\geq 2$  subjects at the same dose level experience similar CSEs considered related to LY3323795;
- 4)  $\geq 2$  subjects at the same dose level have an ophthalmic finding considered related to LY3323795;
- 5)  $\geq 2$  subjects, at any dose of LY3323795, have a QTc reading (mean of 3) that is  $>500$  msec or an increase of  $>60$  msec above the mean QTc control value for at least 2 consecutive time points. The mean QTc control value (mean of 3) is defined as the average of the Day 1, predose ECGs of the corresponding period.

Dosing may continue, if deemed appropriate by the investigator and sponsor, at doses lower than those that resulted in the dose escalation being stopped.

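### Section 3.3 still states an exposure limit ten times the one that governs Part A, and the Part B dose rules carry no explicit exposure threshold

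*Protocol*

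**What the plan says.** **Part A.** Section 5.1.1.1 requires a PK review from Dose 4 onwards, before the next level, "to verify that the projected median exposure does not exceed one tenth the NOAEL exposure established in rats". It gives the limit as a median AUC of 3,450 ng·h/mL and a median Cmax of 214 ng/mL. Section 5.5, under its Part A heading, repeats both figures and says "the anticipated doses may be modified to ensure that median exposures do not exceed one tenth of the rat NOAEL determined in toxicology studies".

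**Whole study.** Section 3.3 describes PK assessment during the study "to ensure that median exposures do not exceed the lowest NOAEL exposure in toxicology studies conducted under GLP (in male rats"). It does not say one tenth.

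**Part B.** Under 5.1.2.1, a Part B dose may not be higher than doses already given and well tolerated in Part A, and "In no case will the doses selected exceed the maximum tolerated dose (MTD) found in Part A". Section 5.5 (Part B) adds: "The maximum dose administered in Part B is intended to be the MTD in Part A, although a lower dose may be selected". The sentence goes on to make the lower dose conditional on what emerging PK/PD data from either part show. Section 7.4.1 defines the MTD: "The highest dose level that is tolerated will be designated as the MTD". Figure SCAA.1 lists "PK data from Part A" among the inputs to Dose B3, and 5.1.1.1 says that the "results of the PK IADs following Doses 4, 5, and 6" will help select Part B doses. None of these Part B statements carries a number for exposure.

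**The concern.** The protocol gives two different figures for one safety limit. A reader who takes 3.3 as the general statement would work to a limit ten times higher than the one in the escalation rules. According to the amendment summary (Appendix 6), the lower figure was adopted after regulator feedback.

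The Part B rules do not settle the matter. The Part A check acts on projected exposure before the next Part A level. Nothing follows the last Part A dose, so no stated threshold is applied to the exposure observed at that dose. If that dose is tolerated it becomes the MTD, whatever its exposure, and the MTD is the intended top dose for Part B. At stake is whether the five active subjects in Cohort 5, healthy volunteers with a lumbar catheter and no expected benefit, stay within the sponsor's own limit by rule or only by judgement.

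**Working it through.** **1. Reproduce the limit.** Table SCAA.2 gives the male-rat NOAEL exposure as AUC 34.5 µg·h/mL and Cmax 2,140 ng/mL.
- AUC: 34.5 × 1,000 / 10 = 3,450 ng·h/mL
- Cmax: 2,140 / 10 = 214 ng/mL

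Both match 5.1.1.1 and 5.5. The 3.3 wording corresponds to 34,500 ng·h/mL and 2,140 ng/mL.

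**2. Find the dose at which the cap is reached.** Section 5.5 predicts AUC 24.5 ng·h/mL at 0.3 mg (90% CI 9.09 to 65.9). Dose proportionality is assumed.
- AUC per mg: 24.5 / 0.3 = 81.7
- Dose at the AUC cap: 3,450 / 81.7 = 42 mg
- At the CI ends: 3,450 / (65.9 / 0.3) = 15.7 mg and 3,450 / (9.09 / 0.3) = 114 mg
- Dose at the Cmax cap, using 0.627 ng/mL at 0.3 mg from Table SCAA.2: 214 / (0.627 / 0.3) = 102 mg, so AUC binds first
- Dose at the full-NOAEL AUC in 3.3: 34,500 / 81.7 = 422 mg

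| Planned dose | Predicted AUC (ng·h/mL) | Share of 3,450 |
|---|---|---|
| 10 mg | 817 | 0.24 |
| 30 mg | 2,450 | 0.71 |
| 100 mg | 8,167 | 2.37 |

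**3. Is the cap likely to decide the last Part A dose?** Reading the 90% CI as log-normal, the log SD is ln(65.9 / 9.09) / 3.29 = 0.602. Before any PK check acts, the chance that the true AUC is above 3,450 is about 0.8% at 10 mg, 28% at 30 mg and 92% at 100 mg. The cap dose therefore falls below 30 mg with probability 28%, between 30 and 100 mg with 64%, and above 100 mg with 8%. PK may well set the top Part A dose before tolerability does. In that case the MTD as defined is a poor stand-in for the exposure limit.

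**4. How often would the last Part A dose prove to be above the cap?** The simulation used six active subjects per level, log-normal AUC, dose proportionality, and 15,000 runs per setting. Doses 0.3 to 10 mg are given; 30 mg and then 100 mg are given only if the projected median is within 3,450. The projection uses either the latest level alone or all levels. The result is the chance that the all-data Part A median at the last dose given exceeds 3,450. The CV is an assumption; the documents give none for between-subject exposure.

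| True AUC | Projection | CV 20% | 30% | 40% | 60% |
|---|---|---|---|---|---|
| Drawn from the protocol's CI | latest level | 3.6% | 4.6% | 6.1% | 7.8% |
| Drawn from the protocol's CI | all levels | 1.5% | 1.8% | 2.1% | 3.0% |
| At the point projection | either | at most 0.2% across all CVs | | | |

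With the true AUC drawn from the CI, the median excess among runs above the cap is 4.0% to 12.7%.

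**5. Part C.** Its dose is at most one tenth of the MTD (5.5), and the predicted interaction is about 4-fold (5.4): 0.1 × 4 = 0.4 of the exposure at the MTD. The gap does not extend to Part C.

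**The case against.** The strongest reply is that Part B already inherits the cap. Its doses must have been covered by Part A, and escalation beyond Dose 4 requires projected exposure within the limit. Section 7.4.1 cites 5.1.2.1 among the places where PK guides dose decisions. Dose B3 takes Part A PK as an input, the sponsor team is unblinded at these reviews, and 5.5 (Part B) expressly provides for a dose below the MTD on PK grounds. Section 5.5 (Part A) also speaks of the upper dose for the study as a whole, and the amendment summary states the one-tenth limit without naming a part. As for 3.3, any exposure that meets one tenth of the NOAEL also meets the NOAEL.

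Most of this stands, and it rules out two stronger readings. A reader might infer that Part B could be given 100 mg at 2.4 times the cap. The documents do not support that: on the protocol's projection, 5.1.1.1 would stop 100 mg in Part A, so it could not be used in Part B. A reader might also infer that a dose known to exceed the cap simply stays the intended top Part B dose. That ignores the rest of the 5.5 (Part B) sentence, since an observed median above the protocol's own limit is an obvious PK reason to go lower.

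What the reply does not supply is a threshold. Choosing a lower dose is permitted rather than required, and no figure says when. The study-wide remark in 5.5 sits under the Part A heading and concerns the escalation. The 3.3 wording may be harmless in operation, but it is the only current exposure statement not tied to one part, and it gives the wrong figure.

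**Conclusion.** The point holds in a limited form. Section 3.3 is inconsistent by a factor of ten with 5.1.1.1 and 5.5 (Part A) and needs correcting on any reading. The Part B rules lack a mandatory exposure threshold for one case: a Part A dose that passed the projection check, was tolerated, and then showed an observed median above 3,450 ng·h/mL or 214 ng/mL.

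That case is uncommon on the planned levels: essentially nil at the protocol's point projection, and about 2% to 8% of simulated trials over its CI. These figures rest on dose proportionality, log-normal exposure, a CV of 20% to 60%, and 30 mg and 100 mg being used without intermediate levels. A last dose sized exactly to the cap would overshoot about half the time by construction, but the protocol plans no such dose. An excess of 4% to 13% remains far below 34,500 ng·h/mL and lies within the uncertainty of a median from a few subjects. This is a gap in a stated limit, not a toxicity signal, and the change is desirable rather than essential.

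**What to change.** 1. In 3.3, replace the full male-rat NOAEL with one tenth of that exposure, and give the two figures.
2. In 5.1.2.1 and 5.5 (Part B), add: *The Part B ceiling is the lower of the MTD and the highest Part A dose whose estimated median AUC and Cmax, from all PK data to date, are at or below 3,450 ng·h/mL and 214 ng/mL.*

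The MTD definition and the stopping rules in 7.4.1 can stay as they are.

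The cost is protocol wording. No new data are needed, because Part A PK is already reviewed for Dose B3. The top Part B dose may be somewhat lower. The aim of cutting CSF Aβ by more than 50% for at least 4 hours should still be within reach: 5.5 models a 90% time-averaged reduction at steady state at an AUC of 1,800 ng·h/mL (90% CI 1,240 to 2,600), and 1,800 / 3,450 = 52% of the cap, with 2,600 / 3,450 = 75% at the upper limit. That model is for steady state and Part B is single-dose, so this indicates room under the cap rather than proving it.
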